# 9.5. Unscheduled Assessments and Early Termination Visits

#### 9.5.1. Unscheduled Assessments

Unscheduled visits occur at any unplanned subject evaluation during study conduct not specified in the Schedule of Events or overall protocol and will be documented and recorded in the database and listings. Unscheduled assessments during study conduct will be inclusive of, but not limited to TDS removals, TDS applications, adhesion assessments, adhesion photographs, and skin tolerability assessments.

#### 9.5.2. Early Termination (ET)

Early Termination (ET) from the study is defined as withdrawal during the Treatment Phase after at least one dose of study drug is administered. The ET Visit is not required for subjects who screen fail before the administration of the first dose of study drug.

If possible, subjects who terminate early will complete all study procedures post-dose study drug (including PK sample collections) before starting ET procedures. The following procedures will

be performed at ET visits:

- 1. Complete physical examination.
- 2. Vital signs (respiratory rate, pulse rate, blood pressure, and oral temperature) after subject has been sitting for a minimum of 3 minutes.
- 3. 12-lead ECG after subject has been in supine position for a minimum of 3 minutes.
- 4. Clinical laboratory tests (chemistry, hematology coagulation, and urinalysis). Samples for clinical laboratory tests at Early Termination can be collected under non-fasted conditions.
- 5. Urine pregnancy tests (for females only)
- 6. Assessment of the Columbia Suicide Severity Rating Scale (C-SSRS), "Since Last Visit" version. If a subject has a clinically significant suicidal ideation based on the C-SSRS assessment, in the opinion of the Investigator, further evaluation and/or preventive intervention steps for suicidal behavior will be taken, at the discretion of the Investigator.
- 7. If applicable, perform skin irritation/tolerability assessments, adhesion assessments and adhesion photographs.
- 8. Review of concomitant medications, treatment and/or therapies.
- 9. Assessment of adverse events.

Subjects will be discharged from the study clinic when the Investigator determines that the subjects are medically stable and, if possible, after all ET procedures are completed.

At the discretion of the Investigator, ensuring the safety of the subjects, any ET procedures that were already performed on the same day as part of the procedures of the current treatment phase, do not need to be repeated.

Subjects who withdraw early from the study and complete the above ET procedures will not return for a Follow-Up Visit. Therefore, the ET Visit is the EOS for these subjects.

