#### 9.7. End of Study (EOS)

The End of Study (EOS) is either the Follow-Up Visit for subjects who complete the Treatment Phase, or the Early Termination Visit for subjects who withdraw early from the study.

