#### 12.8. Adverse Event Assessments

Adverse events (AEs) shall be monitored continuously from the administration of the first dose of study drug until either the Follow-Up or Early Termination visits as noted on the Schedule of Events. AEs will be monitored continuously and solicited using a non-leading question immediately after dosing and at 1, 3, 5, 10, 24 hours post-dose, after all other procedures at each specified time are performed. Definitions and details of AE reporting and documentation are listed in **Section 19**.

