## 16.2. Withdrawal of Subjects Post-Dose Study Drug

If a subject meets withdrawal criteria post-dose during the Treatment Phase, the subject will complete, if possible, all study procedures after the current (last) administration of study drug (including PK sample collections) before starting Early Termination procedures. The subject will be withdrawn and Early Termination procedures will be completed prior to the subject's discharge from the clinic.

At the discretion of the Investigator, ensuring the safety of the subjects, any ET procedures that were already performed on the same day as part of the procedures of the current treatment phase, do not need to be repeated.

The Sponsor may be contacted if clarification is required on a case-by-case basis.

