# **18. ADVERSE EXPERIENCE REPORTING AND DOCUMENTATION**

#### **18.1.** Adverse Events

#### 18.1.1. Recording and Monitoring of Adverse Events

For the purpose of this clinical trial, all Adverse Events will be recorded and monitored for all enrolled subjects from the moment they receive the dose of study drug until they complete the study at the EOS (the Follow-Up visit or the Early Termination Visit).

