6.11.1 Adverse Events

A treatment emergent adverse event (TEAE) is defined as:

- Any AE that has a new onset during the study between the initiation of study drug and the follow-up visit.
- Any pre-existing AE that has worsened in severity on or after the initiation of study drug till the follow-up visit.

The following rules will be used to assign a TEAE to a treatment:

- A TEAE will be assigned to the treatment received immediately before onset.
- Any TEAE reported within Period 1, Day 36, when no treatment is administered, will be attributed to the last treatment received before Day 36 began.
- If the severity of a TEAE increases in a later period the TEAE at the increased severity also will be assigned to the treatment received immediately before the increase in severity.

Page 33 of 61 Confidential

All TEAEs are defined as being definitely, probably, possibly related or unrelated to the study drug. If an AE has missing relationship it is assumed to be definitely related to the study drug for analysis purposes. Additionally, any SAE considered definitely, probably, or possibly related to the study drug will also be classified by the Sponsor as either "expected" or "unexpected" upon review by the medical monitor.

Adverse event severity will be graded as Grade 1: Mild, Grade 2: Moderate, or Grade 3: Severe or Medically Significant but not immediately life-threatening. Maximum severity will be assumed for an AE with missing severity.

All AEs will be coded using the most current version of the Medical Dictionary for Regulatory Activities (MedDRA version 23.1, updated to include activities related to COVID-19) by SOC and PT.

The following tables will be presented for AEs by treatment and overall using the Safety Population:

- Overall incidence and the number of AEs, SAEs, TEAEs leading to withdrawal.
- TEAE by system organ class and preferred term, incidence and number of events
- Treatment related TEAE by system organ class and preferred term, incidence and number of events
- Serious TEAE by system organ class and preferred term, incidence and number of events and "expected or unexpected" classification
- TEAE by system organ class and preferred term by nearest relationship to study drug, incidence and number of events
- TEAE by system organ class, preferred term and maximum severity, incidence
- TEAEs leading to early withdrawal by system organ class and preferred term, incidence

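### Adverse-event recording stops at the early-termination visit, so subjects who leave early are not asked about new non-serious events in the days when completers are

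*Protocol*

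**What the plan says.** **Early terminators.** Protocol 9.5.2 states: "Subjects who withdraw early from the study and complete the above ET procedures will not return for a Follow-Up Visit". Protocol 9.7 defines the end of study as the Follow-Up Visit for completers, "or the Early Termination Visit for subjects who withdraw early from the study".

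**When recording stops.** Protocol 12.8 runs adverse-event monitoring "until either the Follow-Up or Early Termination visits as noted on the Schedule of Events". Protocol 18.1.1 says the same of recording: "until they complete the study at the EOS (the Follow-Up visit or the Early Termination Visit").

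**When ET takes place.** No interval is fixed. Protocol 9.5.2 says: "If possible, subjects who terminate early will complete all study procedures post-dose study drug (including PK sample collections) before starting ET procedures". Protocol 16.2 repeats the request: "the subject will complete, if possible, all study procedures after the current (last) administration of study drug". Note 12 to the Schedule of Events allows for a subject who terminates while still wearing a patch.

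**Completers.** Protocol 6.1 places their Follow-Up Visit 5 ± 2 days after the last oral dose or last patch removal. Protocol 9.6 includes an adverse-event assessment at that visit.

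**What counts as treatment-emergent.** Protocol 17.6 counts new onsets to 5 days after the last dose. SAP 6.11.1 counts onsets "between the initiation of study drug and the follow-up visit". SAP 6.2.3 groups ET assessments with Follow-Up as the End of Study visit.

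**The concern.** The ET procedures in 9.5.2 closely match the Day 109 end-of-treatment list in 9.4.5. For completers the protocol does not stop at that discharge check; it adds a later visit to look at safety again. Early terminators get only the equivalent of the discharge check.

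Donepezil has a half-life of about 70 hours (Protocol 3), so a good part of the drug is still present at ET. A mild or moderate event that starts a day or two later has no scheduled route into the data. Under SAP 6.11.1 it would have been tabulated against the treatment received just before onset. What is at stake is whether adverse events are ascertained comparably in early terminators and completers, and whether collection lasts as long as the protocol's own treatment-emergent window.

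**Working it through.** **1. Subjects who could be affected.** Protocol 17.2 plans about 60 enrolled and 48 completers.
- 60 − 48 = 12, and 12/60 = 20%. Equivalently, 48/(1 − 0.20) = 60.
- The figure of 12 is total planned attrition, so it is a ceiling.

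The plan's power figure reproduces. With CV 29%, the within-subject SD is √ln(1 + 0.29²) = 0.284. The standard error is 0.284 × √(2/48) = 0.058, on 46 degrees of freedom. Exact two-one-sided-test power at a ratio of 1.05 is 0.904, against the stated 90% or more. Nothing below changes it.

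**2. Length of the gap.** Gap = day of the completers' visit minus day of ET, both counted from the last oral dose or patch removal. The completers' visit is on day 3, 5 or 7 (5 ± 2, Protocol 6.1). Three days are possible for ET:
- Day 0: termination on the last exposure day, since finishing procedures first is only asked where possible.
- Day 1: oral dosing with procedures finished. Protocol 12.8 has events "solicited using a non-leading question immediately after dosing and at 1, 3, 5, 10, 24 hours post-dose", so the last scheduled question is at 24 h.
- Day 3: patch with procedures finished, if the skin scores after removal count as post-dose procedures. The last routine score is at 72 h (SAP 6.2.9).

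| ET day | vs day 3 | vs day 5 | vs day 7 |
|---|---|---|---|
| 0 (last exposure day) | 3 | 5 | 7 |
| 1 (oral, 24 h done) | 2 | 4 | 6 |
| 3 (patch, 72 h done) | 0 | 2 | 4 |

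**3. Against the protocol's own window.** For oral dosing, 17.6 runs to day 5. Collection ends 5 − 0 = 5 days short if ET is on day 0, and 5 − 1 = 4 days short if it is on day 1. For patches, 17.6 does not say whether the last dose means application or removal, so I draw no figure from it there.

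**4. Residual drug when recording stops.** Fraction left = 2^(−t/70), assuming a 70-hour half-life, first-order decline, immediate oral absorption and no continued absorption from skin.
- 0 h: 1.00
- 24 h: 0.788
- 72 h: 0.490
- 120 h: 0.305
- 168 h: 0.189

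Recording for an early terminator can therefore stop with 100% (day 0), 79% (day 1) or 49% (day 3) of the level left. Completers are asked at 49%, 30% and 19% (days 3, 5 and 7).

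**5. Do other provisions fill the gap?**
- Protocol 16.1 follows a subject withdrawn for an adverse event until that event resolves or stabilises.
- Protocol 18.3 follows known events, and related serious events for at least 30 days after the last dose.
- Protocol 15 follows irritation until the score is 1 or less.
- Protocol 19 follows pregnancies.

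None schedules a question about a new non-serious event after ET. Several withdrawal reasons in 16.1 involve no adverse event, such as withdrawn consent, non-compliance or social reasons. For those subjects there may be no further contact.

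**The case against.** The strongest reply is that this is a deliberate and internally consistent choice. ET is declared the end of study in two places, recording ends there in explicit terms, and nothing promises later collection. Discharge requires medical stability and, where possible, completed ET procedures, among them an examination, ECG, laboratory tests and an adverse-event assessment. Levels are falling, and Protocol 3 reports no specific safety concern in earlier studies. All of this stands. It makes the point an improvement to the design, not a contradiction in it.

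The size also needs restraint. Subjects withdrawn for adverse events, or with ongoing irritation, stay in contact, so the uncovered group is mainly those who leave for other reasons with nothing ongoing. SAP 6.12 expects most dropouts in the first one or two periods, and Period 1 is entirely the 5 mg/day patch. The oral gap therefore applies to an unknown fraction of the 12. If levels are dose-proportional, as Protocol 3 expects, a 5 mg/day subject at steady state with nothing yet eliminated has about half the 10 mg/day level. That is close to the 0.490 left in a 10 mg/day completer at day 3.

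A reader might also infer that SAP 6.11.1 contains a separate error, because its window closes at a visit early terminators do not have. The documents do not support that. SAP 6.2.3 already treats ET and Follow-Up together as the End of Study visit, which gives a workable end point. Since recording starts at first dose and stops at ET, practically every new onset recorded for these subjects counts as treatment-emergent anyway.

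**Conclusion.** The point holds, and it is minor. New non-serious adverse events that start after ET are not collected, although completers are asked 3 to 7 days after exposure ends. The uncovered interval is 3 to 7 days when ET falls on the last exposure day. With post-dose procedures finished it is about 2 to 6 days after oral dosing and 0 to 4 days after a patch, so in the best patch case there is no gap against the earliest completer visit.

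It concerns an unquantified part of at most about 12 of 60 subjects. The patch figures assume that the 72-hour skin score is treated as a post-dose procedure.

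Two stronger readings should be resisted. The residual-drug fractions describe exposure; they do not show that events are missed, and the documents give no event rate from which to estimate a number. Nor is the bioequivalence conclusion touched: only descriptive safety tables are involved, and no PK endpoint, power or alpha changes.

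**What to change.** - **Protocol 9.5.2:** add one contact for early terminators, by telephone, 5 ± 2 days after the last oral dose or patch removal, to ask about new adverse events.
- **Protocol 12.8 and 18.1.1:** extend monitoring and recording to that contact. ET can remain the end of study in 9.7.
- **SAP 6.11.1:** close the treatment-emergent window for these subjects at the contact or, if they are not reached, at ET, in line with SAP 6.2.3.
- **Reporting:** give the number contacted out of those who terminated early.

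The cost is a few sentences and one call for at most about 12 subjects, with no clinic visit, new procedure or extra staff. The drawback is that some who leave will not be reached, which is why the number contacted should be reported.

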# 9.6. Follow-Up Visit

Subjects who complete the Treatment Phase will return in  $5 \pm 2$  days after the administration of the last dose of study drug for the Follow-Up Visit.

The following procedures will be completed during the Follow-Up Visit:

- 1. Complete physical examination.
- 2. Vital signs after a minimum of 3 minutes of rest (respiratory rate, pulse rate, blood pressure, and oral temperature).

- 3. 12-lead ECG after the subject has been supine at least 3 minutes.
- 4. If applicable, perform skin irritation/tolerability assessments.
- 5. Review of concomitant medications, treatment and/or therapies.
- 6. Assessment of adverse events.

The Follow-Up Visit is the EOS for subjects who will undergo the Follow-Up procedures.

#### 9.7. End of Study (EOS)

The End of Study (EOS) is either the Follow-Up Visit for subjects who complete the Treatment Phase, or the Early Termination Visit for subjects who withdraw early from the study.

## **10. CONCOMITANT MEDICATIONS AND RESTRICTIONS**

Subjects will be instructed not to consume any of the below products; however, allowance for an isolated single incidental consumption may be evaluated and approved by the study Investigator based on the potential for interaction with the study drug, and impact on subject safety and the validity of the study results.

#### **10.1. Concurrent Medication Restrictions**

#### **Restricted Medications:**

- 1. Any OTC medication use within 14 days prior to Day -1 until the End-of-Study Visit without evaluation and approval by the study Investigator. With approval of the Investigator, acetaminophen may be given as needed during the study as rescue medication to treat headaches or other adverse events.
- 2. Subject must not take any prescription medication, with the exception of female hormonal contraceptives, from 14 days prior to Day -1 until the End-of-Study Visit without evaluation and approval by the Investigator.

All other concomitant medications will be prohibited unless its use is deemed necessary in a medical emergency. Concomitant use of prescription or nonprescription medications, including reasons for use, will be reviewed, and recorded on the eCRF from the Screening Period through the Follow-up Period.

Allowed concurrent medications can be taken with water if needed, irrespective of the water restrictions before and after administration of study drug.

#### **10.2.** Dietary Restrictions

While subjects are in the research clinic, the following dietary restrictions will be followed:

- 1. Subjects must not take any herbal or dietary supplements (e.g., St. John's Wort, Milk Thistle, etc.) within 14 days prior to Day -1 until the End-of- Study Visit.
- 2. Subjects must not consume beverages and foods containing alcohol or caffeine/xanthine from 48 hours prior to Day -1 until after discharge on Day 109. Alcohol and caffeinated beverages will not be available while in the research clinic.
- 3. Water Consumption: Water will be allowed ad libitum up to 1 hour prior to dose administration. For Treatment C (Aricept 10 mg), after 1 hour following dose administration, subjects may drink water ad libitum. Fluids during the predose light meal are allowed.
- 4. Food Consumption: While housed in the research clinic, subjects will receive meals at regularly scheduled times. No food sharing will be permitted. Standard meals will be provided at appropriate times. Calories will be spread across the day. Mealtimes may be adjusted to not interfere with study procedures such as blood draws for pharmacokinetics.

## **10.3.** General Restrictions

- 1. Subject must not engage in strenuous activities such as exercise or sports within 24 hours prior to Day -1 until the End-of-Study Visit.
- 2. No more than 1 shower a day is permitted. Subjects must avoid having the water spray directly on the patch. Water running over the patch is allowed. The patch should be patted dry after the shower.
- 3. Subject must not donate blood (one pint or more) from 30 days or plasma from 14 days prior to Day -1 until the End-of-Study Visit. It is recommended that blood/plasma donations not be made for at least 30 days after the End-of-Study Visit.
- 4. Subjects must not smoke or use tobacco products from 6 months prior to Day -1 until the End-of-Study Visit. Subjects must refrain from use of all nicotine products (including e-cigarettes, pipes, cigars, chewing tobacco, nicotine topical patches, nicotine gum, or nicotine lozenges) from Screening until the End-of-Study Visit.
- 5. Female subjects must utilize one of the allowed forms of birth control listed in the Inclusion Criteria (Section 8.2.1).
- 6. Following all TDS applications, subjects will remain seated in chairs without the following back support: pillows, soft padding, blankets, or similar; for at least the first 2 hours, except

when they are supine or standing for study procedures. Subjects will then resume normal activity. During the first 2 hours post dose, subjects may be allowed to rise for brief periods under supervision (e.g., in order to use the toilet facilities). However, should AEs occur at any time, subjects may be placed in an appropriate position or will be permitted to lie down on their side.

 Following oral drug administration (Treatment C) subjects will remain seated, except as otherwise required for study procedures or personal needs, for the first 4 hours after dosing. Subjects will not be allowed to lie down, except as directed by clinical staff secondary to adverse events, for the first 4 hours after dosing.

# **11. INVESTIGATIONAL PRODUCT**

#### **11.1. Active Pharmaceutical Ingredients**

CorplexTM Donepezil Transdermal Delivery System (TDS) is a matrix type transdermal patch manufactured for a 7-day application.

#### **11.2.** Pharmaceutical Treatments

**Treatment A (Test):** 5 mg/day Donepezil TDS manufactured with the commercial process applied weekly (within  $\pm 1$  hour of application time on Day 1) for 5 consecutive weeks (7-day wear each). All subjects will receive Treatment A in Period 1. The patch will be removed on the morning of Day 36.

At the start of Period 2, subjects will be randomized to one of the following treatments in Period 2. Subjects will receive the alternate treatment in Period 3. Randomization to the 2 treatment sequences will be stratified by gender.

**Treatment B (Test):** 10 mg/day CorplexTM Donepezil TDS manufactured with the commercial process applied weekly (within  $\pm 1$  hour of application time on Day 1) for 5 consecutive weeks (7-day wear each).

**Treatment C (Reference):** 10 mg Aricept® donepezil (1 x 10 mg/day tablet) administered QD for 35 consecutive days (within  $\pm 1$  hour of dosing time on Day 1). This is the Reference Listed Drug (RLD).

#### **11.3. Supply of Study Drug**

The Sponsor (or designee) will ship study drug to the investigational site. The study drug shipment(s) will be shipped after site activation. All other drug products needed for the conduct of the study (such as medications to treat Adverse Events) will be commercially available products obtained by the research clinic.

# 11.4. Packaging and Labeling

The investigation product will be packaged and labeled appropriately, according to the appropriate FDA regulations. See the Pharmacy Manual for details of packaging and labeling.

# 11.5. Materials Control

Once received and labeled by the onsite pharmacist or designee for use in the study, the drugs will be considered study drug material. The pharmacist or designee will maintain adequate records of the receipt, dispensing, return or other disposition of the drug, including dates, quantity, serial numbers, expiration dates, as appropriate. Reasons for any departure from the expected regimen will be documented. These documents will be made available to regulatory agency inspectors upon request. The Investigator will not supply study drug to anyone other than those named as sub-investigators on FDA Form 1572, designated site staff, and subjects in the study.

# 11.6. Storage of Study Drug

Study drug for Treatment A and B will be stored at a controlled; refrigerated temperature (2-8°C). The pharmacy will remove the TDS from 2-8°C refrigerated storage on the day before application and no more than 24 hours prior to application, and stored at controlled room temperature of 20-25°C (68-77°F) with excursions allowed between 15° and 30°C (59° and 86°F). Transient spikes up to 40°C are permitted as long as they do not last for more than 24 hours. Study drug will be stored in a safe, secure area with limited, controlled access in accordance with all local, state, and federal regulations. Investigational products must not be frozen. The Investigator will ensure that adequate precautions are taken, including storage of the study drug in a securely locked, substantially constructed cabinet, or other securely locked, substantially constructed enclosure, access to which is limited, to prevent theft or diversion of the substance into illegal channels of distribution.

The investigational product(s) must be stored as indicated. Deviations from the storage requirements, including any actions taken, must be documented and reported to the Sponsor. Once a deviation is identified, the investigational product must be quarantined and not used until the Sponsor provides documentation of permission to use the investigational product.

